6.5 Overdose

A maximum tolerated dose has not been established for osimertinib. An overdose is any dose which exceeds the daily dose that is defined in the clinical study protocol.

Such overdoses should be recorded as follows:

- An overdose with associated AEs is recorded as the AE diagnosis/symptoms on the relevant AE modules in the eCRF and on the Overdose eCRF module.
- An overdose without associated symptoms is only reported on the Overdose eCRF module.

If an overdose on an AstraZeneca study drug occurs in the course of the study, then the Investigator or other site personnel inform appropriate AstraZeneca representatives immediately, or **no later than 24 hours** of when he or she becomes aware of it.

The designated AstraZeneca representative works with the Investigator to ensure that all relevant information is provided to the AstraZeneca Patient Safety data entry site.

For overdoses associated with a SAE, the standard reporting timelines apply, see Section [6.4](#).
For other overdoses, reporting must occur within 30 days.

6.6 Pregnancy

All pregnancies and outcomes of pregnancy should be reported to AstraZeneca during the course of the study and within 6 weeks of the last dose of osimertinib.

6.6.1 Maternal exposure

If a patient becomes pregnant during the course of the study IP should be discontinued immediately.

Pregnancy itself is not regarded as an AE unless there is a suspicion that the IP under study may have interfered with the effectiveness of a contraceptive medication. Congenital abnormalities/birth defects and spontaneous miscarriages should be reported and handled as SAEs. Elective abortions without complications should not be handled as AEs. The outcome of all pregnancies (spontaneous miscarriage, elective termination, ectopic pregnancy, normal birth, or congenital abnormality) should be followed up and documented even if the patient was discontinued from the study.

If any pregnancy occurs in the course of the study or within 6 weeks of the final dose of the IP, then the Investigator or other site personnel informs the appropriate AstraZeneca representatives within 1 day, ie, immediately, but no later than 24 hours of when he or she becomes aware of it.

The designated AstraZeneca representative works with the Investigator to ensure that all relevant information is provided to the AstraZeneca Patient Safety data entry site within 1 or 5 calendar days for SAEs (see Section [6.4](#)) and within 30 days for all other pregnancies.

The same timelines apply when outcome information is available.

6.6.2 Paternal exposure

Pregnancy of the patient's partners is not considered to be an AE. However, the outcome of all pregnancies (spontaneous miscarriage, elective termination, ectopic pregnancy, normal birth or congenital abnormality) should if possible be followed up and documented.

To capture information about a pregnancy from the partner of a male patient, the male patient's partner consent must be obtained to collect information related to the pregnancy and outcome; the male patient should not be asked to provide this information. A consent form specific to this situation must be used. The outcome of any conception occurring from the date of the first dose until 4 months after dosing ends should be followed up and documented.

6.7 Medication Error, Drug Abuse, and Drug Misuse

6.7.1 Timelines

If an event of medication error, drug abuse **or** drug misuse occurs during the study, then the Investigator or other site personnel informs the appropriate AstraZeneca representatives within **one day**, ie, immediately but **no later than 24 hours** of when they become aware of it.

The designated AstraZeneca representative works with the Investigator to ensure that all relevant information is completed within **one** (initial fatal/life-threatening or follow-up fatal/life-threatening) **or 5** (other serious initial and follow-up) **calendar days** if there is an SAE associated with the event of medication error, drug abuse, or misuse (see Section **6.4**) and **within 30 days** for all other events.

6.7.2 Medication Error

For the purposes of this clinical study, a medication error is an **unintended** failure or mistake in the treatment process for an AstraZeneca study drug that either causes harm to the patient or has the potential to cause harm to the patient.

A medication error is not lack of efficacy of the drug, but rather a human or process related failure while the drug is in control of the study site staff or patient.

Medication error includes situations where an error.

- Occurred
- Was identified and intercepted before the patient received the drug
- Did not occur, but circumstances were recognised that could have led to an error

Examples of events to be reported in clinical studies as medication errors:

- Drug name confusion
- Dispensing error, eg, medication prepared incorrectly, even if it was not actually given to the patient
- Drug not administered as indicated, eg, wrong route dose (error greater than +/- 10%), or wrong site of administration
- Drug not taken as indicated, eg, tablet dissolved in water when it should be taken as a solid tablet
- Drug not stored as instructed, eg, kept in the fridge when it should be at room temperature

- Wrong patient received the medication (excluding IVRS/IWRS errors)
- Wrong drug administered to patient (excluding IVRS/IWRS errors)

Examples of events that **do not** require reporting as medication errors in clinical studies:

- Errors related to or resulting from IVRS/IWRS - including those which lead to one of the above listed events that would otherwise have been a medication error
- Patient accidentally missed drug dose(s), eg, forgot to take medication
- Accidental overdose (will be captured as an overdose)
- Patient failed to return unused medication or empty packaging
- Errors related to background and rescue medication, or SoC medication in open-label studies, even if an AstraZeneca product, patient failed to return unused medication or empty packaging.

Medication errors are not regarded as AEs, but AEs may occur as a consequence of the medication error.

If a medication error occurs in the course of the study, then the Investigator or other site personnel informs the appropriate AstraZeneca representatives within 1 day, ie, immediately but **no later than 24 hours** of when he or she becomes aware of it.

The designated AstraZeneca representative works with the Investigator to ensure that all relevant information is completed within 1 or 5 calendar days if there is a SAE associated with the medication error (see Section [6.4](#)) and within 30 days for all other medication errors.

6.7.3 Drug Abuse

Drug abuse is the persistent or sporadic **intentional**, non-therapeutic excessive use of AstraZeneca study drug for a perceived reward or desired non-therapeutic effect.

The full definition and examples of drug abuse can be found in Appendix [B 1](#).

6.7.4 Drug Misuse

Drug misuse is the **intentional** and inappropriate use (by a study patient) of AstraZeneca study drug for medicinal purposes outside of the authorised product information, or for unauthorised AstraZeneca study drug, outside the intended use as specified in the protocol and includes deliberate administration of the product by the wrong route.

The full definition and examples of Drug Misuse can be found in Appendix [B 1](#).

6.8 Management of Investigational Product-Related Toxicities

Dose adjustment for AEs should be in accordance with the following table:

Table 4 Osimertinib Dose Adjustment Information for Adverse Reactions

Target organ	Adverse reaction	Dose modification
Pulmonary	Interstitial lung disease/pneumonitis	Permanently discontinue osimertinib
Cardiac	QTc interval greater than 500 msec on at least 2 separate ECGs	Withhold osimertinib until QTc interval is less than 481 msec or recovery to baseline if baseline QTc is more than 481 msec within 3 weeks of interruption, then restart at a reduced dose (40 mg) or at 80 mg (at the discretion of the Investigator, to allow for situations where causality in relation to osimertinib may be difficult to determine)
	QTc interval prolongation with signs/symptoms of serious arrhythmia	Permanently discontinue osimertinib
Cutaneous	Stevens-Johnson Syndrome and toxic epidermal necrolysis (TEN)	Permanently discontinue osimertinib
Blood and lymphatic system	Aplastic anaemia	Permanently discontinue osimertinib
Other	Grade 3 or higher adverse reaction	Withhold osimertinib for up to 3 weeks
	If Grade 3 or higher adverse reaction improves to Grade 0-2 after withholding of osimertinib for up to 3 weeks	Osimertinib may be restarted at the same dose (80 mg) or a lower dose (40 mg)
	Grade 3 or higher adverse reaction that does not improve to Grade 0-2 after withholding for up to 3 weeks	Permanently discontinue osimertinib

Note: The intensity of clinical adverse events graded by the NCI CTCAE version 4.0.
ECG = electrocardiogram; CTCAE = Common Terminology Criteria for Adverse Event; NCI = National Cancer Institute; QTc = QT interval corrected for heart rate; TEN = toxic epidermal necrolysis.

If a patient experiences a CTCAE Grade 3 or higher adverse reaction, and/or unacceptable toxicity, including a dose-limiting toxicity (DLT), not attributable to the disease or disease-related processes under investigation, dosing will be interrupted, and supportive therapy administered as required in accordance with local practice/guidelines.

If a toxicity resolves or reverts to \leq CTCAE Grade 2 within 3 weeks of withholding osimertinib, treatment with osimertinib may be restarted at the same dose or a lower dose

using the rules below for dose modifications ([Table 5](#)) and with discussion and agreement with the AstraZeneca Study Team Physician as needed. There will be no individual modifications to dosing schedule in response to toxicity, only potential dose reduction or dose interruption.

If the toxicity does not resolve to \leq CTCAE Grade 2 after 3 weeks of withholding osimertinib, then the patient should be withdrawn from the study and observed until resolution of the toxicity.

Table 5 Dose Interventions

Intervention	Osimertinib dose
Starting dose	80 mg
Reduced dose – 1	40 mg

On resolution of toxicity within 3 weeks:

If an AE subsequently requires dose interruption, osimertinib may restart at the same dose or the reduced dose, on resolution/improvement of the AE at the discretion of the Investigator.

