Should patients with HBV infection be included, patients are only eligible if they meet all the following criteria:

- Demonstrated absence of HCV co-infection or history of HCV co-infection.
- Demonstrated absence of HIV infection.
- Patients with active HBV infection are eligible if they are:
 - Receiving anti-viral treatment for at least 6 weeks prior to study treatment, HBV DNA is suppressed to < 100 IU/mL and transaminase levels are below upper limit of normal (ULN).
- Patients with a resolved or chronic infection HBV are eligible if they are:
 - Negative for HBsAg and positive for hepatitis B core antibody [anti-HBc IgG]. In addition, patients must be receiving anti-viral prophylaxis for 2 to 4 weeks prior to study treatment.

or

- Positive for HBsAg, but for > 6 months have had transaminases levels below ULN and HBV DNA levels below < 100 IU/mL (ie, are in an inactive carrier state). In addition, patients must be receiving anti-viral prophylaxis for 2 to 4 weeks prior to study treatment. Refer to Section [3.5](#).

Should patients with HIV infection be included, patients are only eligible if they meet ALL of the following criteria:

- Undetectable viral RNA load for 6 months
- CD4+ count of > 350 cells/ μ L
- No history of AIDS-defining opportunistic infection within the past 12 months
- Stable for at least 4 weeks on the same anti-HIV medications.

16. Patients who have had a surgical procedure unrelated to the study within 14 days or major surgery within 1 month prior to the administration of the study drug; patients with a significant traumatic lesion (as judged by the Investigator that would risk patient safety) during the 4 weeks prior to starting the administration of the study drug; patients who have not recovered from the side effects of any major surgery; or patients who might need major surgery during the course of the study.
17. Past medical history of ILD, drug-induced ILD, radiation pneumonitis which required corticosteroid treatment, or any evidence of clinically active ILD.
18. Any of the following cardiac criteria:
 - Mean resting QT interval corrected for heart rate (QTc) > 470 msec, obtained from 3 ECGs, using the screening clinic ECG machine-derived QTc value.
 - Any clinically important abnormalities in rhythm, conduction or morphology of resting ECG, eg, complete left bundle branch block, third-degree heart block, and second-degree heart block.

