 - Any factors that increase the risk of QTc prolongation or risk of arrhythmic events such as heart failure, hypokalaemia, hypomagnesaemia, hypocalcaemia, congenital long QT syndrome, family history of long QT syndrome or unexplained sudden death under 40 years of age in first degree relatives or any concomitant medication known to prolong the QT interval.
19. Spinal cord compression, symptomatic and unstable brain metastases except for those patients who have completed definitive therapy and have had a stable neurological status for at least 2 weeks after completion of definitive therapy. Patients may be on corticosteroids to control brain metastases if they have been on a stable dose for 2 weeks (14 days) prior to the start of study treatment and are clinically asymptomatic.

20. Refractory nausea and vomiting, chronic gastrointestinal diseases, inability to swallow the formulated product or previous significant bowel resection that would preclude adequate absorption of osimertinib.
21. Inadequate bone marrow reserve or organ function as demonstrated by any of the following laboratory values:
 - Absolute neutrophil count $< 1.5 \times 10^9/\text{L}$.
 - Platelet count $< 100 \times 10^9/\text{L}$.
 - Haemoglobin (Hb) $< 90 \text{ g/L}$.
 - Alanine aminotransferase (ALT) > 2.5 times the ULN if no demonstrable liver metastases or > 5 times ULN in the presence of liver metastases.
 - Aspartate aminotransferase (AST) > 2.5 times ULN if no demonstrable liver metastases or > 5 times ULN in the presence of liver metastases.
 - Total bilirubin (TBL) > 1.5 times ULN if no liver metastases or > 3 times ULN in the presence of documented Gilbert's Syndrome (unconjugated hyperbilirubinaemia) or liver metastases.
 - Creatinine > 1.5 times ULN concurrent with creatinine clearance $< 50 \text{ mL/min}$ (measured or calculated by Cockcroft and Gault equation); confirmation of creatinine clearance is only required when creatinine is > 1.5 times ULN.
22. Female patients who are breastfeeding.
23. Patients currently receiving (or unable to stop use prior to receiving the first dose of study treatment) medications or herbal supplements known to be potent inducers of cytochrome (CYP) 3A4 (at least 3 weeks prior; [Appendix E](#)). All patients must try to avoid concomitant use of any medications, herbal supplements, and/or ingestion of foods with known inducer effects on CYP3A4.
24. Patient unwilling to undergo a biopsy at the time of disease progression.

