5.2.2 Physical examination

A physical examination will be performed and include an assessment of the following: general appearance, skin, head and neck (including ears, eyes, nose, and throat), respiratory, cardiovascular, abdomen, lymph nodes, thyroid, musculoskeletal (including spine and extremities), and neurological systems.

5.2.3 *Electrocardiogram*

5.2.3.1 *Resting 12-lead electrocardiogram*

Twelve-lead ECG will be performed at the visits indicated in the Study Plan.

Twelve-lead ECGs will be obtained after the patient has been resting semi-supine for at least 10 minutes prior to times indicated. All ECGs should be recorded with the patient in the same physical position. For each time point one ECG recording should be taken. A standardised ECG machine should be used and the patient should be examined using the same machine throughout the study if possible.

After the paper ECG has been recorded, the Investigator or designated physician will review the ECG and may refer to a local cardiologist if appropriate. A copy of the ECG should be filed in the patient's medical records. If an abnormal ECG finding at screening or baseline is considered to be clinically significant by the Investigator, it should be reported as a concurrent condition. For all ECGs, details of rhythm, ECG intervals and an overall evaluation will be recorded.

If there is a clinically significant abnormal ECG finding during the treatment period, this should be recorded on the AE eCRF, according to standard AE collection and reporting processes. A 28-day follow-up assessment will be required if an on-treatment assessment was abnormal at the time of discontinuation of study therapy, to confirm reversibility of the abnormality.

5.2.4 *Echocardiogram/Multigated acquisition scan*

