6.8.2 QTc prolongation

In light of the potential for QT changes associated with osimertinib, electrolyte abnormalities (hypokalaemia, hypomagnesaemia, hypocalcaemia) must be corrected to be within normal ranges prior to first dose and electrolyte levels monitored during study treatment.

Patients with QT interval corrected using Fridericia's correction (QTcF) prolongation to > 500 msec should have study treatment interrupted and regular ECGs performed until resolution to < 481 msec, or recovery to baseline, if baseline QTcF is ≥ 481 msec and then restarted at a reduced dose of 40 mg, or 80mg at the discretion of the Investigator. If the

toxicity does not resolve to \leq CTCAE Grade 1 within 21 days, the patient will be permanently withdrawn from study treatment.

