^b Values determined from comprehensive review (internal to AZ) of each compound's PK half-life and determination of the washout period.

^c Estimated value as PK of arsenic trioxide has not been studied.

AZ = AstraZeneca; PK = pharmacokinetics; TdP = Torsades de Pointes.

E 3 Other TdP risk categories

Patients receiving drugs that prolong QT interval or may increase the risk of TdP from other TdP risk categories can be enrolled, notwithstanding other exclusions and restrictions, if these drugs are considered essential for patient management and the patient has been stable on therapy. Close monitoring of ECGs and electrolytes is recommended.

Patients with **congenital long QT syndrome** are excluded from this study.

During study treatment and for a period of 2 weeks after discontinuing study treatment, if it is considered essential for patient management to co-administer drugs known to prolong QTc interval, **regardless of TdP risk category**, close monitoring of ECGs and electrolytes is recommended.

Appendix F Guidelines for Evaluation of Objective Tumour Response Using RECIST 1.1 Criteria (Response Evaluation Criteria in Solid Tumours)

F 1 Introduction

This appendix details the implementation of RECIST 1.1 guidelines ([Eisenhauer et al 2009](#)) for the D5161C00003 study with regards to Investigator assessment of tumour burden including protocol-specific requirements for this study.

F 2 Definition of Measurable, Non-Measurable, Target and Non-Target Lesions

Only patients with measurable disease at baseline should be included in the study. Measurable disease is defined by the presence of at least one measurable lesion which has not been previously irradiated and not chosen for biopsy during the Screening Period.

Measurable:

A lesion, not previously irradiated and not chosen for biopsy during the Screening Period, that can be accurately measured at baseline as ≥ 10 mm in the longest diameter (except lymph nodes which must have short axis ≥ 15 mm) with CT or MRI and which is suitable for accurate repeated measurements. If only one measurable lesion exists, it is acceptable to be used (as a target lesion) as long as it has not been previously irradiated and baseline tumour assessment scans are done at least 14 days after the screening biopsy is performed.

Non-measurable:

- All other lesions, including small lesions (longest diameter < 10 mm or pathological lymph nodes with ≥ 10 to < 15 mm short axis at baseline*)

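### Protocol Table 4 and Section 6.8.2 give different QTc triggers for interrupting osimertinib, so one reading above 500 msec can lead to opposite dosing actions

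*Protocol*

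**What the plan says.** Protocol Section 6.8 opens by saying that dose adjustment for adverse events follows Table 4. The cardiac row of that table acts on "QTc interval greater than 500 msec on at least 2 separate ECGs". Drug is then withheld until QTc falls below 481 msec, or returns to baseline where baseline QTc was more than 481 msec.

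Section 6.8.2, under the same heading, has its own instruction, written for QTcF: "prolongation to > 500 msec should have study treatment interrupted and regular ECGs performed until resolution to < 481 msec". For a patient who started at 481 msec or higher, a return to the starting value is accepted instead. The section gives no number of ECGs for the trigger and does not refer to Table 4.

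On ECG collection, Section 5.2.3.1 states: "For each time point one ECG recording should be taken". Table 2 places ECGs at every treatment visit: every 8 weeks from Cycle 7 to Day 1277, then every 10 weeks.

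Three other passages touch the same subject:

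- Exclusion criterion 18 (Section 3.2) bars a mean resting QTc above 470 msec, "obtained from 3 ECGs, using the screening clinic ECG machine-derived QTc value".
- The same criterion bars "any concomitant medication known to prolong the QT interval".
- Appendix E 3 says "Patients receiving drugs that prolong QT interval or may increase the risk of TdP from other TdP risk categories can be enrolled". The sentence continues with a notwithstanding clause about other exclusions and restrictions, and with two conditions: the drug is essential and the patient is stable on it.

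**The concern.** A site that obtains one ECG above 500 msec has two current instructions. Section 6.8.2 tells it to interrupt; Table 4 tells it to act only when a second ECG is also above the limit. Neither says how soon a repeat must be done, or what happens to dosing in the meantime.

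Patients with the same reading could be handled differently from site to site. The consequence carries into the analysis. SAP Section 4.2.8 tabulates dose interruptions and their reasons, and SAP Section 3.3.3 subtracts interruption time from intended exposure to obtain actual exposure. These outputs would mix two triggers, and the ECG summary in SAP Section 4.2.10.4 would not reveal which was used, because its only QTc category is QTcF above 470 ms.

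**Working it through.** The documents state no figure to reproduce, and the point needs no power or sample-size calculation. The check sets the passages side by side.

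**Step 1. The two rules**

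| Element | Table 4 | Section 6.8.2 |
|---|---|---|
| Measure | QTc, formula not named | QTcF |
| Limit | above 500 msec | above 500 msec |
| ECGs needed before interruption | two or more, separate | none stated beyond the reading itself |
| Target for resolution | below 481 msec | below 481 msec |
| Baseline that opens recovery to baseline | above 481 msec | 481 msec or more |

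The repeated ECGs in Section 6.8.2 come after the interruption, to follow resolution. They do not confirm the trigger.

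**Step 2. One reading above 500 msec.** Take a patient with one ECG on which QTc and QTcF both exceed 500 msec, and no repeat yet. Table 4: 1 of the 2 required ECGs, so no interruption. Section 6.8.2: condition met, so interruption. The actions are opposite.

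**Step 3. Does the schedule supply the second ECG?** One recording per time point gives 1 of the 2. Nominal time to the next scheduled ECG (protocol Table 2):

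- Cycle 1: Day 1 to 8 and Day 8 to 15, 7 days each; Day 15 to 29, 14 days.
- Cycles 2 to 6: 28 days (29, 57, 85, 113, 141, 169).
- Cycle 7 to Day 1277: 8 × 7 = 56 days.
- After Day 1277: 10 × 7 = 70 days.

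An earlier unscheduled ECG is possible. Section 5.2.3.1 has clinically significant ECG findings recorded as adverse events, and Table 2 footnote i asks for an ECG with any cardiac adverse event. Neither sets a deadline or says what to do with dosing while waiting.

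**Step 4. The measure.** Entry uses a machine-derived QTc, Table 4 uses QTc, and Section 6.8.2 uses QTcF. Where the correction formulas differ, the same tracing can fall on different sides of 500 msec. The documents do not say that the three are the same.

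**Step 5. The recovery threshold.** More than 481 and at or above 481 msec differ only for a baseline of exactly 481 msec, so this difference is small.

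**Step 6. Minor mismatches**

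- The entry mean needs 3 ECGs, while Section 5.2.3.1 schedules one recording per time point and Table 1 has a single screening ECG entry.
- The recovery clause opens 481 − 470 = 11 msec above the highest screening mean that criterion 18 admits.
- Criterion 18 excludes QT-prolonging co-medication, and the introduction to Section 3 allows no exceptions to eligibility, while Appendix E 3 allows some such patients to enrol.

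**The case against.** The best defence is that Table 4 governs. Section 6.8 says that dose adjustment follows the table, and Section 6.8.2 never says that a single ECG suffices; it may only have left out a qualifier. That is a fair reading, but it does not remove the problem. Section 6.8.2 is a direct instruction in its own right, names a different measure and does not defer to the table. An investigator who follows it literally is complying with the protocol.

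The defence is stronger on the minor points, where a reader might infer more than the documents support:

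- *That the 3-ECG mean cannot be obtained.* Criterion 18 does not require the three at one time point, and screening runs from Day −28 to Day −1. Three ECGs at separate times satisfy both passages. The wording is unclear, not unworkable.
- *That entry rules out a baseline of 481 msec.* Criterion 18 caps the mean screening QTc. The protocol does not define the ECG baseline, and SAP Section 3.3.1 takes the last value before dosing. A Day 1 pre-dose ECG, or a QTcF value, could reach 481 msec in a patient whose screening mean was 470 msec or less. The clause sits awkwardly with the entry limit but can be reached.
- *That Appendix E 3 flatly contradicts criterion 18.* Its notwithstanding clause can be read as an express carve-out. It then conflicts with the no-exceptions rule in Section 3, so the text still needs tidying.

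Finally, enrolment is past. Section 8.1 assumes 12 months of recruitment, and the SAP's visit windows run to Day 2387. Changes to entry wording would alter no enrolment.

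**Conclusion.** The point holds for Table 4 against Section 6.8.2. The current text gives two triggers for the same event, differing in the number of ECGs and in the QT measure, with a small further difference in the recovery threshold. On a literal reading, one QTcF above 500 msec interrupts dosing under one passage and not under the other. From Cycle 7 the next scheduled ECG is nominally 56 or 70 days away.

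What is affected is patient protection, and the interpretation of reported dose interruptions and actual exposure. The primary endpoint, the primary analysis set and the sample size are not.

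A reader might want a probability that the two rules disagree. The documents do not support one: they give no within-patient QT variability and no rate of readings above 500 msec. Table 4 also does not require its two ECGs to come from one visit. The conclusion rests on the wording alone. It assumes that no site instruction outside these documents already settles the trigger. The mismatches on entry ECGs, the 481 msec baseline and co-medication are minor.

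**What to change.** The sponsor's clinical team must reconcile Table 4 and Section 6.8.2 so that both state the same trigger (number of ECGs and QT measure) and the same recovery condition. This review takes no position on which rule is right. A site clarification should follow for patients still on treatment.

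In the same edit, align the 3-ECG entry mean with Section 5.2.3.1, the 481 msec recovery clause with the 470 msec entry limit and a defined ECG baseline, and criterion 18 and the no-exceptions rule with Appendix E 3. If the wording cannot be changed before the study closes, the clinical study report should say which trigger sites applied when it presents QT-related interruptions.

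The cost is protocol wording and one communication to sites. No new data collection or change to the primary analysis follows from the reconciliation itself.

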3.6.1 Procedures for discontinuation of a patient from investigational product

At any time, patients are free to discontinue IP or withdraw from the study (ie, IP and assessments; see [Section 3.7](#)) without prejudice to further treatment. A patient that decides to discontinue IP will always be asked about the reason(s) and the presence of any AEs. If possible, they will be seen and assessed by an Investigator(s). AEs will be followed up (see [Section 6](#)); all study drugs should be returned by the patient.

Study procedures related to serious adverse events (SAEs) and anticancer treatment must be captured until the patient no longer has RECIST 1.1 assessments (disease progression or permanent withdrawal from the study).

If a patient is withdrawn from the study, see [Section 3.7](#).

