3.7.2 Withdrawal of informed consent

Patients are free to withdraw from the study at any time (IP and assessments) without prejudice to further treatment. Withdrawal of consent should be clearly documented in the patient notes and in the eCRF.

A patient who withdraws consent will always be asked about the reason(s) and the presence of any AEs. The Investigator will follow-up AEs outside of the clinical study.

If a patient withdraws from participation in the study, then his/her enrolment code cannot be re-used. Withdrawn patients will not be replaced.

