4.3 Follow-up Period

1. All patients will be followed up for safety at approximately 28 days.
2. All patients will be followed up for RECIST 1.1-defined progression.
3. All patients will be followed up for subsequent anticancer treatment/death.

4.3.1 28 days after treatment discontinued

As a minimum, telephone contact should be made with the patient 28 days (+ 7 days) following the discontinuation of osimertinib (last dose of IP) to collect new AEs and follow-up on any ongoing AEs and concomitant medications (including any subsequent anticancer treatment). Refer to Section [6.3.1](#) for full details on AE recordings during follow-up.

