4.3.2 Follow-up for RECIST 1.1-defined progression

Patients who discontinue study drug for reasons other than RECIST 1.1-defined progression will continue RECIST assessments every 8 weeks (\pm 7 days) (relative to study enrolment) up to 3.5 years (1277 days) and every 10 weeks (\pm 14 days) from Day 1278 to objective progression.

In addition to tumour assessments, the following assessments are also required during this follow-up period:

- First subsequent anticancer therapy (including surgical) after discontinuing osimertinib or death
- WHO performance status (once at start of first subsequent anticancer therapy)
- Concomitant medication and procedures (only in the first scheduled progression follow-up visit)
- AEs (only in the first scheduled progression follow-up visit)

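### Protocol 6.8 takes patients with unresolved toxicity off the study, where the rest of the protocol only stops osimertinib and keeps following them

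*Protocol*

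**What the plan says.** Protocol 6.8 interrupts osimertinib for a Grade 3 or higher adverse reaction or other unacceptable toxicity. If three weeks off drug do not bring the toxicity to Grade 2 or lower, "then the patient should be withdrawn from the study and observed until resolution of the toxicity".

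Table 4, in the same section, has a row for the same situation, "Grade 3 or higher adverse reaction that does not improve to Grade 0-2 after withholding for up to 3 weeks", and the action in that row is to discontinue osimertinib permanently. Section 3.6 and the paragraph after 6.8.5 likewise only bar a restart of treatment. The parallel QTc rule in 6.8.2 takes the patient off study treatment, not off the study.

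Elsewhere, stopping the drug and leaving the study are separate acts. Section 3.6.1 states that "patients are free to discontinue IP or withdraw from the study (ie, IP and assessments", and Section 3.7.2 repeats the gloss: "Patients are free to withdraw from the study at any time (IP and assessments". For follow-up, Section 4.3 states "All patients will be followed up for RECIST 1.1-defined progression" and "All patients will be followed up for subsequent anticancer treatment/death". Section 4.3.2 adds: "Patients who discontinue study drug for reasons other than RECIST 1.1-defined progression will continue RECIST assessments".

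**The concern.** Two instructions cover the same patient and lead to different follow-up. Under Table 4 the patient stops osimertinib and moves into progression follow-up. Under the 6.8 sentence the patient leaves the study, and only observation of the toxicity is kept.

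The difference matters because PFS (Protocol 8.4.2, SAP 3.2.2.1) counts progression or death whether or not the patient has stopped therapy or started another. It needs scans after a toxicity stop. If those scans end because of toxicity, the censoring is tied to something that may be related to prognosis. DoR takes its end date from PFS, and TFST depends on continued collection of subsequent therapy and death.

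**Working it through.** No sample size or power figure is involved, so the check sets the sections side by side.

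1. **Is the trigger the same?** Yes. The 6.8 text and Table 4 both concern a Grade 3 or higher reaction still above Grade 2 after three weeks of withholding. The 6.8 text also mentions unacceptable toxicity, but anything already at Grade 2 or lower would not meet its withdrawal condition.

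2. **What does each place require for that trigger?**
   - 6.8 text: leave the study.
   - Table 4: stop osimertinib permanently.
   - 3.6 and the paragraph after 6.8.5: no restart of study treatment.

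   One place against three.

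3. **Does leaving the study end assessments?** Section 3.6.1 requires capture of SAE and anticancer-treatment data "until the patient no longer has RECIST 1.1 assessments (disease progression or permanent withdrawal from the study". Permanent study withdrawal is thus named as an end point for RECIST, and for the capture tied to it. Section 6.3.3 also records the action taken with the drug separately from whether the adverse event led to study withdrawal.

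4. **What contradicts the literal reading?**
   - RECIST continues after the drug stops in five places: 4.3, 4.3.2, 5.1.1, Table 2 footnote k and Appendix F 4.1.
   - Follow-up for subsequent therapy or death continues in three: 4.3, 4.3.2 and Table 2 footnote m.
   - No section says which instruction prevails.

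5. **What happens to each endpoint if a site follows 6.8 literally?**
   - PFS: censored at the last evaluable RECIST assessment. A known death still counts if it falls within the two-missed-visit limit in SAP 3.2.2.1 (119, 126, 147 or 168 days after the last assessment, depending on when that assessment was).
   - DoR: censored at the PFS censoring date (SAP 3.2.2.3).
   - TFST: censored at the earlier of the last known alive date and study termination (SAP 3.2.2.6).
   - TTD: little affected, since stopping the drug is itself the event.
   - Primary marker proportion: largely unaffected. Under Table 2 footnote f, a patient who stops osimertinib before progression has no second biopsy in any case. The exception is a patient treated beyond progression and not yet biopsied, who could lose the second biopsy by being withdrawn.

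6. **Can the effect be sized?** No. The documents give neither the number of patients meeting the 6.8 rule nor their hazard of progression after stopping. If that hazard were higher than in patients still followed, early censoring would make the PFS curve too favourable; if lower, too unfavourable.

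**The case against.** The strongest reply is that this is one loose phrase which the rest of the protocol overrides. Section 6.8 opens by making its table the rule for dose adjustment, and the table stops only the drug. Section 3.7, on criteria for withdrawal, covers screen failure and withdrawal of consent, not toxicity. The gloss that study withdrawal covers assessments is written for a patient's own choice, so applying it to an investigator's action is an inference. The wording of 6.8.2 also suggests what was meant. All of this supports drug discontinuation as the likely intent. None of it tells a site to disregard an explicit sentence in the section on toxicity management.

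A second reply is timing. Protocol version 7.0 is dated April 2023 and Section 9.3 ends the study by Q2 2023, so a wording change alone would protect few patients. That stands, and it is why the fix also looks back.

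Stronger readings are tempting but not supported:

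- A reader might infer that scans were stopped and that PFS is biased. No passage shows either.
- A reader might try to size the loss from scan spacing. Spacing describes the time between the last scan and withdrawal, which exists for anyone censored between scans. It does not measure follow-up lost afterwards.
- A reader might infer that the missing scans would be reported as important protocol deviations. SAP 2.2 leaves classification to review before database lock, and a site following 6.8 would be obeying a protocol instruction.

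**Conclusion.** The contradiction is in the current body text and is not reconciled anywhere. Confidence is high on the wording conflict; no effect on results is shown. The conclusion that follow-up would end rests on reading study withdrawal in 6.8 as Section 3.6.1 uses the term.

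At stake are PFS, DoR and TFST, which are secondary and descriptive in a single-arm study. Any early censoring may be informative, but its size and direction cannot be determined. A reader might infer that the primary endpoint is wholly untouched; the case of a patient treated beyond progression and awaiting biopsy prevents that. This is a minor point, worth correcting because the instruction is wrong as written and the remedy is small.

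**What to change.** In Protocol 6.8, replace *withdrawn from the study* with *permanently discontinued from osimertinib*. Add that RECIST assessment until progression, and follow-up for subsequent therapy and death, continue under Section 4.3 unless the patient withdraws consent.

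Because the study is near its end, also list the patients whose adverse-event record shows study withdrawal caused by the event (the field in Protocol 6.3.3) and who were censored for PFS, DoR or TFST. If there are none, the listing documents that the sentence had no effect on these endpoints. If there are some, their number and censoring dates can be reported with the results.

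Cost: the rewording belongs in a protocol version, which Section 10.5 makes subject to ethics approval and, where applicable, regulatory approval. The listing uses data already collected but is a small new output. SAP 4.2.1 and 4.2.9.2 plan summaries, and the withdrawal count in SAP 4.2.2 covers only patients with an evaluable baseline biopsy. The listing cannot recover scans that were never done.
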